**Title: Predicting treatment response in Chronic Pancreatitis using Quantitative Sensory Testing**

**Date: January 3, 2018**

## Predicting treatment response in Chronic Pancreatitis using Quantitative Sensory Testing

### Objective:

Endoscopic therapy or surgery for treatment of pain is typically offered to chronic pancreatitis (CP) patients with pancreatic ductal strictures and/or stones. However, clinical pain symptoms correlate poorly with pancreatic ductal morphology, response to endoscopic or surgical therapy is unpredictable, and the rationale for invasive therapies is often questioned.

Quantitative sensory testing (QST) can map the pain system; the technique is based on the rationale that different neural pathways and networks can be explored using standardized stimulation and simultaneous recording of the evoked pain response by psychophysical and/or objective methods. We hypothesize that endoscopic or decompressive surgical therapy is most effective for patients with local sensitization without systemic or abnormal activation of the central pain system. Our objective is to distinguish phenotypes characterized by segmental sensitization of the pancreatic viscerotome (T10), and systemic sensitization with pathological central pain processing including augmented temporal summation and impaired descending pain inhibition.

### Aims:

- Aim 1) Investigate the association between QST profiles and demographic and clinical characteristics including depression and anxiety questionnaires in patients with suspected or definite CP.
- Aim 2) Investigate if the QST profile of the individual patient can be used to predict the clinical outcome of endoscopic or surgical treatment in patients with suspected or definite CP.
- Aim 3) Investigate the temporal evolution and association of QST profiles and clinical pain scores after endoscopic or surgical treatment in patients with suspected or definite CP.

### Background

[figure not shown]
Treatment of pain in patients with CP is challenging and different treatments are offered to patients based on tradition and knowledge from other pain syndromes. In some patients, treatment is based on pathogenesis and when obvious duct changes, stones and strictures are present (large duct disease), surgery and endoscopic procedures with and without extracorporeal shock wave lithotripsy (ESWL) has been used successfully (Löhr et al. 2017). These procedures are to some extent mechanism based, as they aim to improve the flow of pancreatic juice or reduce inflammation. However, recent studies have *not* found a relation between the micro- or macrostructure and the pain intensity and therefore the pathophysiological evidence can be questioned (Frøkjær et al. 2013; Wilcox et al. 2015). It should also be noted that the marked placebo effect of the different treatment cannot be neglected and future research should aim to identify individual responders and if possible (such as in endoscopic procedures with stent placement) to include a sham arm in the studies. On the other hand, the many case reports and observational studies of pain improvement after invasive procedures cannot be neglected. Furthermore, evidence from studies in somatic tissues with peripheral nerve injury and painful polyneuropathy, also suggest that primary afferent input is critical for maintaining the neuropathic pain (Haroutounian 2014), and as such this provides a mechanistic rationale for treatment in patients with duct obstruction.

The *Nijmegen Aalborg Screening QST Paradigm (NASQ)* has been developed in collaboration between groups in Holland and Denmark to replace cumbersome and highly technological methods for visceral pain stimulation with a simpler paradigm that can be used at bedside. The method uses in its original design quantitative sensory testing (QST) with tetanic electrical and pressure stimulation at different dermatomes in order to unravel the pain system. Furthermore, it includes assessment of descending inhibition with pressure stimulation before and after a “conditioning stimulus” with the hand immersed into ice water (conditioned pain modulation, CPM). In order to detect changes in the pain system with NASQ we have previously used postoperative pain as a model, as the painful event (the surgery) is planned and controlled, and therefore the changes in the nociceptive system can be followed

systematically. After surgery, it has been shown that the initial changes in pain processing (using the NASQ) in the days after surgery can predict who will develop chronic postsurgical pain (Wilder-Smith 2015). For example, we recently showed that early postoperative hyperalgesia to pressure stimulation in the first days after surgery was an independent risk factor for development of chronic pain (van Helmond et al. In preparation 2016).

In CP, we have used NASQ to detect differences in generalised sensitization (overall difference between the blue and green curves in figure 1) as well as changes in the sensation between different dermatomes (for example the hyperalgesia at T10 in figure 1) together with assessment of CPM. Hence, we have showed that patient with increased sympathetic drive have increased pain to QST in general (Buscher et al. 2010), and the degree of generalised sensitization correspond with the MANNHEIM severity index (the more diseased, the more pain) as well as response to splanchnicectomy (Bouwense et al. 2011; Bouwense et al. 2013). The methods have also been used to guide treatment, as selective sensitization at the pancreatic dermatome (T10) rather than generalized sensitization was shown to predict the effect of pregabalin (Olesen et al. 2013). We have also shown that patients with CP suffer from deficient descending inhibition as reflected in CPM. Drugs such as tapentadol and venlafaxine may potentiate this mechanism in patients with neuropathy (Yarnitski et al. 2012; Niesters et al. 2015). We therefore believe that these drugs are helpful in many patients with pain due to pancreatitis, where a large fraction is thought to have neuropathic pain (Drewes et al. 2008).

Notably, QST profiles from CP patients have been reported only in Europeans to date: no data exist at this time on CP patients in the United States.

[figure not shown]
*Figure 1. The different dermatomes tested (left) and a profiling of controls and patients with different degree of sensitization to pressure pain stimulation (right)*

**Methodological aspects:** The pressure and electrical stimulations were previously shown to be reproducible in patients with CP (figure 2) whereas the CPM was not (Olesen et al. 2012). On the other hand, this is an inherent problem with all methods to evoke descending inhibition (even in healthy volunteers) and is not restricted to CP. As many patients are reluctant towards the electrical stimulation and the methods also are technically more demanding, we compared in a pilot study pain assessment between electrical and pressure stimulation at different dermatomes. As can be seen in figure 3 there is limited gain using electrical stimulation as compared with pressure when the pain tolerance thresholds are used. In the newest version of NASQ we also added pinprick stimulation with the possibility to address “temporal summation”. This is a method that corresponds to “wind-up” in preclinical studies and is suitable to study central sensitization. When temporal summation is used in patients with a sensitized pain system they show increased pain response to repeated stimuli at the same intensity delivered with a frequency above 0.3 Hz. Temporal summation has also been shown to reflect central sensitization in patients with pain due to CP (Dimcevski et al. 2007). We therefore suggest that the modified NASQ will consist of the following:

- 1) the mechanical pain with the pressure device at the different dermatomes shown in figure 1
- 2) temporal summation with the standardized pin-prick instrument
- 3) assessment of CPM with pressure (same device as 1) before and after immersion of the hand in ice-water.

This is doable in about 20 min after training, but to ensure reasonable repeatability it needs to be in the hand of few persons. The QST shall be supported by questionnaires to -

[figure not shown]
- 4) assess depression (using e.g., Hospital Anxiety and Depression Scale, Bjelland et al. 2002) and
- 5) situational catastrophizing after the cold water test (Grosen et al. 2016).

*Figure 2. Reproducibility of pressure pain at the pain detection threshold (PDT, left) and pain tolerance threshold (PTT, right) – for details, see Olesen et al. 2012*

Tetanic electi

Pressure s, mula, on

*Figure 3. Recent pilot studies comparing the pain profile in controls and patients between different dermatomes to electrical (left) and pressure (right) stimulations.*

### Significance:

The study may allow us to phenotype patients based on their QST findings in order to better understand and treat the pain syndromes that occur in the setting of CP. It may also allow us to predict the response of phenotyped patients to endoscopic and surgical interventions for CP. We would anticipate further clinical trials with this technique to more accurately understand these pain syndromes and elucidate patterns in other populations.

### Study Participants:

- 1) Subjects with no pancreatic disease and no abdominal pain, or patients with a diagnosis of functional dyspepsia.

#### *Inclusion Criteria:*

- Subjects are 18 years or older in age
- Subjects must be able to read and understand the study information.
- Personally signed and dated informed consent document indicating that the subject has been informed of all pertinent aspects of the study.
- Subject is willing and able to comply with the scheduled visits, questionnaires, treatment plan, and other study procedures.

***Exclusion criteria:***

- Subjects with evidence or history of medical or surgical disease of importance for this study as judged by investigator.
- Subjects suffering from painful conditions that make them unable to distinguish the pain associated with CP from chronic pain of other origins.
- Subjects with known pregnancy at the time of enrolment.
- Subjects who have previously undergone surgical intervention on their pancreas.

**2) Suspected CPs**

***Inclusion Criteria***

- Subjects are 18 years or older in age
- Subjects with a) Indeterminate CP (Cambridge 1 or 2 on CT scan or MRI/MRCP) who have abdominal pain without prior history of AP, or b) those with acute (AP) or recurrent acute pancreatitis (RAP) who have recovered from their attack(s) of AP, whose imaging studies are either normal or show changes consistent with Cambridge classification of 1 or 2, and they have ongoing abdominal pain. Both diabetic and non-diabetic subjects will be allowed to enter the study.
- Subjects must be able to read and understand the study information.
- Subjects must suffer from abdominal pain suspected to be pancreatic origin with an intensity above 3 on the visual analogue scale (VAS, where 0=no pain and 10= intolerable pain), and meet the criteria for chronic pain (pain  $\geq$  3 days per week for at least 3 months).
- Personally signed and dated informed consent document indicating that the subject has been informed of all pertinent aspects of the study.
- Subjects willing and able to comply with the scheduled visits, questionnaires, and other study procedures.

***Exclusion Criteria***

- Subjects with evidence or history of medical or surgical disease of importance for this study as judged by investigator.
- Subjects suffering from painful conditions other than pancreatitis or SOD type 1 or 2 that make them unable to distinguish the pain associated with pancreatitis or SOD from chronic pain of other origins.
- Subjects with known pregnancy at the time of enrolment.
- Subjects who have previously undergone surgical intervention on their pancreas.

**3) Definite Chronic Pancreatitis -**

***Inclusion Criteria***

- Subjects are 18 years or older in age
- Subjects will have a prior confirmed diagnosis of CP on CT scan or MRI/MRCP according to Cambridge Classification (grade 3 or 4). Both diabetic and non-diabetic subjects will be allowed to enter the study.
- Subjects must be able to read and understand the study information.
- Personally signed and dated informed consent document indicating that the subject has been informed of all pertinent aspects of the study.
- Subjects willing and able to comply with the scheduled visits, questionnaires, and other study procedures.

***Exclusion Criteria***

- Subjects with evidence or history of medical or surgical disease of importance for this study as judged by investigator.
- Subjects suffering from painful conditions other than pancreatitis or SOD type 1 or 2 that make them unable to distinguish the pain associated with pancreatitis or SOD from chronic pain of other origins.
- Subjects with known pregnancy at the time of enrolment.
- Subjects who have previously undergone surgical intervention on their pancreas.

**4) Sphincter of Oddi Dysfunction (SOD) Type 1 or Type 2**

***Inclusion Criteria***

- Subjects are 18 years or older in age
- Subjects have prior diagnosis of Type 1 or Type 2 Sphincter of Oddi Dysfunction (subjects with biliary pain accompanied by biochemical features of transient biliary tract obstruction including elevated transaminases, alkaline phosphatase, or conjugated bilirubin; may also be accompanied by biliary or pancreatic ductal dilation on imaging)
- Subjects must be able to read and understand the study information.
- Personally signed and dated informed consent document indicating that the subject has been informed of all pertinent aspects of the study.
- Subjects willing and able to comply with the scheduled visits, questionnaires, and other study procedures.

***Exclusion Criteria***

- Subjects with evidence or history of medical or surgical disease of importance for this study as judged by investigator.
- Subjects suffering from painful conditions other than pancreatitis or SOD that make them unable to distinguish the pain associated with pancreatitis or SOD from chronic pain of other origins.
- Subjects with known pregnancy at the time of enrolment.
- Subjects who have previously undergone surgical intervention on their pancreas.

\*\*Note: Women who become pregnant during the course of the study can no longer participate in QST testing.

**Study Procedures:**

**Baseline Testing:**

All subjects will complete a basic questionnaire at baseline with assistance of a study coordinator or physician investigator which will collect information on demographics, pain characteristics, and information related to their pancreatic health. Subjects will also complete questionnaires on quality of life

(PROMIS Global health Scale and EORTC-QLQ-C30), pain (modified brief pain inventory-short form (mBPI-sf)), psychological impact of pain (Hospital Anxiety and Depression Scale (HADS)) and situational catastrophizing (PCS). It will take approximately 30-60 minutes for subjects to complete the baseline questionnaires.

All subjects will also undergo QST testing at baseline. The procedures are described below in the section entitled “Experimental endpoints (quantitative sensory testing – QST).”

**Followup Testing:**

As part of their regular medical care, some subjects may undergo Endoscopic Ultrasound (EUS), Endoscopic Retrograde Cholangiopancreatography (ERCP), Extracorporeal Shock Wave Lithotripsy (ESWL), surgery, laboratory and imaging studies, and medical treatment. We will review medical records to collect data on these variables prior to enrolment and during the course of the study.

Follow-up testing will be limited to subjects who undergo endoscopic treatment or surgery for the pancreatitis or for SOD. These subjects will fill out a pain diary for 7 days prior to their intervention, as well as for seven days before each follow-up research visit at 1 month, 3 month, and 6 months post-intervention. The pain diary is designed to assess pain intensity and dynamics over time, and is based on a 0-10 NRS rating scale. Both the median and maximal pain for the last 24 hours is registered. It will take approximately 5 minutes per day for subjects to complete the pain diary. These subjects will also undergo QST testing at each follow-up visit at 1 month, 3 months, and 6 months. Lastly, these subjects will fill out the same baseline questionnaires (PROMIS, EORTC-QLQ-C30, mBPI-sf, HADS, PCS), and additionally the Patient’s Global Impression of Change (PGIC) questionnaire for assessment of change in symptoms over time.

**Study Timeline:** Study procedures at baseline and during follow-up and which groups of study subjects will complete individual procedures

	Baseline	Follow-up day 30 post- intervention	Follow-up day 90 post- intervention	Follow-up day 180 post- intervention
QST Testing	All Subjects	Subjects who underwent invasive intervention	Subjects who underwent Invasive intervention	Subjects who underwent invasive intervention
Standardized Patient Questionnaires (PROMIS, EORTC, HADS, BPIsf, PCS)	All Subjects	Subjects who underwent invasive intervention (Add PGIC)	Subjects who underwent invasive intervention (Add PGIC)	Subjects who underwent invasive intervention (Add PGIC)
Pain Diary for 7 days prior		Subjects who underwent invasive intervention	Subjects who underwent invasive intervention	Subjects who underwent invasive intervention
Personal medical history	All Subjects	Collect changes from subjects who	Collect changes from subjects who	Collect changes from subjects who

[figure not shown]
		underwent invasive intervention	underwent invasive intervention	underwent invasive intervention
--	--	---------------------------------	---------------------------------	---------------------------------

\***Intervention: endoscopic therapy or surgery**

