#### **Clinical Outcomes:**

The primary clinical endpoint will be:

- QST profile of subjects with Definite or Suspected CP, SOD, Functional Dyspepsia, and controls

The secondary clinical endpoint will be:

- In subjects undergoing endoscopic or surgical treatment - The absolute and percentage change from baseline in ratings of average pain in the past week at day 90 using a daily pain diary based on a 0-10 numerical rating scale (NRS). A percentage change of  $\geq 30\%$  is considered clinically significant.

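### Does the Study Timeline table leave the day-90 pain endpoint without a baseline diary?

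*Protocol*

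**What the plan says.** Followup Testing limits post-baseline work to subjects who have endoscopic treatment or surgery for pancreatitis or SOD. For them it states "These subjects will fill out a pain diary for 7 days prior to their intervention", and continues "as well as for seven days before each follow-up research visit at 1 month, 3 month, and 6 months post-intervention".

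The Study Timeline table follows directly. Its caption gives its scope as "Study procedures at baseline and during follow-up and which groups of study subjects will complete individual procedures". The columns are Baseline and days 30, 90 and 180 after intervention. In the diary row the Baseline cell is empty and the three follow-up cells name subjects who had an invasive intervention. A footnote defines the term: "Intervention: endoscopic therapy or surgery".

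Baseline Testing, which applies to all subjects, does not list the diary. The pain instrument it names is the mBPI-sf.

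Clinical Outcomes sets the secondary endpoint for treated subjects as the absolute and percentage "change from baseline in ratings of average pain in the past week at day 90 using a daily pain diary", with a change of at least 30% counted as clinically significant.

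**The concern.** The text and the table give different numbers of diary weeks, and the week missing from the table is the one that cannot be replaced. A diary for the seven days before a procedure cannot be filled in afterwards. Without it, a subject has no diary baseline, so the absolute change, the percentage change and the 30% criterion cannot be computed from the diary. The mBPI-sf taken at baseline is a different instrument from the one the endpoint names.

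This is the only treatment-response endpoint that Clinical Outcomes defines, and Aim 2 is about predicting the outcome of treatment. Staff often schedule from a table rather than from prose. A table whose caption claims to cover baseline as well as follow-up might be taken as complete.

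**Working it through.** No sample size, power or error rate is involved. The check is a count, followed by a reading of the two places side by side.

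**Count per treated subject**

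| Source | Before intervention | Before follow-up visits | Weeks | Days |
|---|---|---|---|---|
| Followup Testing, text | 1 | 3 | 1 + 3 = 4 | 4 × 7 = 28 |
| Study Timeline table, diary row | 0 | 3 | 0 + 3 = 3 | 3 × 7 = 21 |

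The difference is 1 week, or 28 − 21 = 7 days. The day-90 change needs two weeks: the one before the intervention and the one before day 90. The table shows one of these and the text requires both.

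**Is the empty cell real?** Yes, as far as the available text shows. The diary row keeps the same five-column layout as the QST and questionnaire rows. The visible break in the table comes lower down, in the medical history row.

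**Do the two places conflict?** A conflict needs two instructions that cannot both be followed.

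1. The table's Baseline column is the visit that all subjects attend; the other rows carry the entry for all subjects there. The diary is asked only of subjects who go on to an intervention, so that entry would be wrong in the diary row.
2. The text ties the first diary week to the date of the intervention, not to the baseline visit. Intervention is part of regular care and reaches only some subjects, so the two dates need not coincide. The row label places each diary in the week before its column's visit. A filled Baseline cell would therefore suggest the week before the baseline visit, which the text does not ask for.
3. The remaining columns all fall after the intervention. The pre-intervention week belongs in none of the four columns.

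The table is therefore silent on that week and does not exclude it. Both places can be followed together by collecting the four weeks in the text, three of which the table also displays.

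**Does the endpoint have a baseline?** Under the text, treated subjects complete one diary week before treatment. It is the only pre-treatment diary in the Protocol, so it is the natural baseline for the day-90 change.

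The Protocol also refers to a timeline figure (Figure 4), which is not reproduced. Nothing here relies on what it shows.

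**The case for a change.** The best case for a change is that the pre-intervention week appears in a single sentence, under a heading about follow-up. It is absent from both places where staff would look for pre-treatment procedures: Baseline Testing and the table. The table's caption claims baseline scope, so the table is incomplete on its own terms. An analysis plan cannot restore diaries that were never collected. At least 60 subjects undergoing endotherapy are planned and the analysis is per protocol, so avoidable losses would hurt. The repair would be cheap and would add no burden, because the text already asks for the week.

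Much of this stands. The omission is real, it is not a reading artefact, and a missed week would be lost for good.

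What does not stand is the step from omission to a fault in the plan. The harm arises only if staff work from the table and disregard the paragraph immediately above it, where this diary week is the first procedure listed for treated subjects. The documents give no basis for estimating how often that would happen. The setting makes it less likely: the study runs in one institution's clinics and hospitals, with a study team that also provides the clinical care and a coordinator or physician investigator doing the testing. The primary endpoint, the QST profile, is untouched.

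**Conclusion.** No change to the plan is needed. The Study Timeline table leaves out one of the four diary weeks that the text requires (21 of 28 days shown). This is an omission from a summary table and not a competing instruction. A team that follows the Protocol as written collects the pre-intervention week and has a diary baseline for the day-90 absolute change, percentage change and 30% criterion. Adding a column or a footnote would be harmless tidying that repeats an existing requirement.

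This rests on two assumptions: that the paragraph governs where the table is silent, and that analysts take the only pre-treatment diary week as baseline. Both are the ordinary reading. The conclusion covers only whether a pre-treatment diary week is provided for; it does not endorse the endpoint's definition in other respects.
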